9.2 Screening Procedures

10 All participants that accept to volunteer will be logged into a screening log associated with the trial. I will confirm the volunteers' health conditions through basic communication. If they cannot meet the criteria, they will be excluded from this project.

10.1 Randomization Procedures (if applicable)

There is no randomisation in this study as all participants will undergo the same process of scanning and recording.

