6.1 Study/Trial Design

This clinical trial will be conducted on 40 participants, each will receive an occlusal devices according to the grouping below. Group

Group	Group A	Group B	Group C	Group D
Criteria	Without digital facebow at ICP	With digital facebow at ICP	Without digital facebow at RAP	With digital facebow at RAP

The clinical and the lab steps:

This clinical trial will need 2 clinical visits:

VISIT ONE:

1-Participant information and informed consent.

Before participation, all participants will be provided with a detailed informed consent form outlining the purpose of the study, the procedures involved, potential benefits, and risks. Participants will be given the opportunity to ask questions before providing written consent.

2-Dental photography including Frontal, Right buccal, Left buccal, Upper occlusal, Lower occlusal views.

3- Digital facebow using the **AxioSnapMount Facebow-Germany**. It typically consists of adjustable earpieces and a bite fork, which are attached to the patient head, the bite fork is inserted into the patient's mouth, and the patient is guided to bite down into occlusion, Once the bite position is scanned, the AxioSnapMount facebow is removed from the patient's head. And the data are transferred as STL file into the program.

4- Digital impression of upper and lower teeth using **Intraoral Scanner (IOS) (Primescan, Sirona)**. Clinical conditions at the time of scanning the patient will be IOS calibrated before each scan according to the manufacture's recommendations, operatory temperature is at room temperature, Optragate will be used to separate the cheeks and saliva suction at the beginning of each arch scan and operatory light will be turned off. The IOS start on the occlusal of the maxillary right second molar, continues along the occlusal surfaces of the adjacent teeth to the left maxillary second molar, continues toward the buccal side of the same left maxillary second molar to the buccal side of the right second molar, and ends with a scan of the lingual side of the same molar to the left maxillary second molar, continues toward the buccal side of the same left maxillary second molar to the buccal side of the right second molar, and ends with a scan of the lingual side of the same molar to the left maxillary second molar.

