9.1 Participant recruitment

- Recruitment research sheets to advertise about the project and will be distributed and advertised. Clinical records will be examined by the to assess eligibility prior to the clinic. Eligible participants or those for whom clarification is required will be approached by their contacts to discuss study participation. Interested participant will have the study explained to them and be provided with an information sheet and given the opportunity to ask questions. Those who agree to take part will then have their eligibility confirmed and informed consent taken prior to participation in the trial. Following consent, baseline clinical assessments will be performed, and the volunteers randomised. We will keep a record of the number approached and the number of participants who are eligible and agree to participate in the trial. Reasons for excluding participants and reasons for nonparticipation will be recorded.

- Participant will be gifted with amazon vouchers of 50 pounds.

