12.3 Access to the data set

The data will be accessed by the research team and the dental lab which will design and prepare the occlusal splints.

13 Statistical considerations.

The sample size should be 30 per each group but because of limited finance and time we decided to do 10 per each group.

13.1 Sample size calculation.

The participant number will be 40 and 40 splints will be fabricated scanned before and after the adjustment for each group.

For the best statistics result the sample size should be 30 but because of the limited time as a PhD student, limited finance, and recourses. Since the literature had studies on digital facebow as clinical reports without comparisons we decided to use 10*4 as the sample size.

- References Some studies about the volumetric changes using the geomatric software as

Alvaro et al did the trial with 31 participant each received 2 splints.

Blasi Á, Henarejos-Domingo V, Palacios-Bañuelos R, Aparicio C, Roig M. Comparison accuracy of digital and analog method using milled occlusal splints. *J Esthet Restor Dent.* 2023 Oct;35(7):1103-1112. doi: 10.1111/jerd.13039. Epub 2023 Mar 21. PMID: 36942721.

Tiwu et al recruited 30 patients and divided them in two groups; each 15 received a different splint ($\alpha=.05$) ($P>.05$)

Tiwu Peng, Zhikang Yang, Teng Ma, Mindi Zhang, Guanghui Ren, Comparative evaluation of the volume of occlusal adjustment of repositioning occlusal devices designed by using an average value digital articulator and the jaw movement analyser *Journal of Prosthetic Dentistry*, 2023.

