13.2 Statistical analysis

Recruitment and Retention

Information on the patients approached to enter the study will be analysed descriptively (Numbers of: patients approached, patients eligible, patients randomised, and patients retained). Reasons for nonentry into the trial will be assessed. Patient drop-out data will be collected to calculate retention rates and identify reasons for non-completion. The number and proportion of participants who did not complete the trial overall will be reported. Reasons for non-completion will be analysed descriptively.

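### Section 10.1 rules out randomisation on a ground that covers only Visit 1, while sections 9.1 and 13.2 say participants are randomised; the four-group comparison has no stated protection against selection or time confounding.

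*Combined protocol and SAP*

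**What the plan says.** Three sections address allocation, and they disagree.

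- Section 10.1 (Randomization Procedures): "There is no randomisation in this study as all participants will undergo the same process of scanning and recording".
- Section 9.1 (Participant recruitment): "Following consent, baseline clinical assessments will be performed, and the volunteers randomised".
- Section 13.2 (Statistical analysis) lists the counts to be reported, including "patients eligible, patients randomised, and patients retained".

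The heading of 13.3.1 also refers to breaking a randomisation code, but the text beneath it describes none.

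On the design, section 6.1 says: "This clinical trial will be conducted on 40 participants, each will receive an occlusal devices according to the grouping below". The groups are A (ICP, no facebow), B (ICP with facebow), C (RAP, no facebow) and D (RAP with facebow). Section 13 sets the group size, "because of limited finance and time we decided to do 10 per each group", and 13.1 gives the total: "we decided to use 10*4 as the sample size".

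The synopsis plans an ANOVA of means across the four groups and mentions no covariate adjustment. Section 10.2 says the trial cannot be blinded. Its only other measure against bias is a single experienced operator for the scanning, helped by a consultant.

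**The concern.** The reason in 10.1 does not support its conclusion. It is true that every participant has the facebow, RAP and ICP records taken at Visit 1. The groups separate afterwards, when the lab uses some of those records and not others to make the splint. That step is the intervention, and having identical records taken beforehand does not make the four sets of ten people comparable.

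The null hypothesis in section 5.1 concerns differences between bite-registration methods, and it is tested between groups. Without random allocation, a difference in the volume of adjustment may reflect:

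- **who was put in each group**, for example the size of a participant's RAP-ICP discrepancy or the number of missing teeth; or
- **when they were treated**, for example if the operator's adjustment technique changes with experience.

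As written, the groups could be filled in recruitment order, or chosen by a researcher who has already seen the scans. The text excludes neither. Two teams following different sections of this protocol would run two different trials, and non-random allocation cannot be undone once the data are in.

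**Working it through.** **Step 1. Is this a between-participant comparison?**

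- Group size: 10; number of groups: 4 (sections 13 and 13.1). 10 × 4 = 40, which reproduces the stated total.
- Participants: 40; splints: 40 (section 13.1). 40 / 40 = 1 splint per participant.
- Section 13.1 also says "The participant number will be 40 and 40 splints will be fabricated scanned before and after the adjustment for each group", and the last three words could be read as 40 splints in each group. That would be 4 × 40 = 160 splints and would contradict both the stated 10 per group and 10 × 4.
- If every participant received all four splints, 40 participants would need 160 splints, or 40 splints would serve only 10 participants. Neither fits.

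So the design is parallel-group, and participants do not act as their own controls.

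**Step 2. Is an allocation rule given elsewhere?** Sections 6.1, 9.1, 10.1, 10.2, 13, 13.1 and 13.2 give no sequence, method, order or concealment.

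**Step 3. What could follow if 10.1 is applied literally?** The documents give no outcome SD and no time trend, so this step is an illustration. Its assumptions are:

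- groups filled in order A, B, C, D, ten at a time;
- normal outcome with SD 1 and no true method effect;
- a linear drift of total size *d* SD from participant 1 to participant 40;
- tests at the 5% level.

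Participant *i* is shifted by *d*(*i* − 1)/39. The group mean shifts are therefore 4.5*d*/39, 14.5*d*/39, 24.5*d*/39 and 34.5*d*/39.

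- Spurious difference, D minus A: 30*d*/39 = 0.77*d*.
- One-way ANOVA, F on 3 and 36 df. The deviations from the overall mean are ±15*d*/39 and ±5*d*/39, so the noncentrality is 10 × 2 × (225 + 25)*d*²/39² = 3.29*d*².
- ICP (A+B) versus RAP (C+D): the spurious difference is 20*d*/39 = 0.513*d* and its standard error is √(1/20 + 1/20) = 0.316, so the noncentrality is 1.62*d*. The plan does not name this contrast as a test. It is shown because the synopsis endpoint sets RAP against ICP.

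Simulated false-positive rates:

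| Total drift (SD) | D − A bias (SD) | ANOVA, filled in order | ANOVA, randomised 10/10/10/10 | ICP v RAP contrast, filled in order |
|---|---|---|---|---|
| 0 | 0 | 5.0% | 4.9% | 5.1% |
| 0.5 | 0.38 | 9.8% | 4.9% | 12.4% |
| 1.0 | 0.77 | 26.5% | 5.3% | 35.2% |
| 1.5 | 1.15 | 55.5% | 4.8% | 65.8% |

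The ANOVA columns use 20,000 simulated trials. A separate run of 40,000 gave 4.9%, 9.6%, 26.7% and 56.0% for the ANOVA filled in order, and it supplied the contrast column. The noncentral F and t distributions with the noncentralities above agree: at *d* = 1 they give about 27% and 35%.

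**The case against.** The contradiction between sections cannot be argued away, but several points limit what may be built on it.

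- **The rates are hypothetical.** Nothing says groups will be filled in sequence, and no drift is given. Strict sequential filling is close to the worst case for a time trend; alternating allocation would largely balance one. An experienced operator may show little learning effect, although section 10.2 claims that experience for scanning and not for adjusting splints. This stands: the table shows a risk left open, not this trial's expected error rate. Alternation would still be predictable, so it would not prevent selection.
- **No one is said to choose groups after seeing scans.** True. Nothing prevents it either.
- **The flowchart in 6.2 could not be read in the copy reviewed** and might show an allocation step. It could not reconcile 10.1 with 9.1.
- **Eligibility narrows the differences between participants.** No more than one missing tooth per quadrant, a stable dentition and no TMD diagnosis all help. They do not limit the RAP-ICP discrepancy.
- **The remedy has side effects.** Releasing allocations only to the lab may leave the operator unaware of the group, which sits badly with the blinding sentence in 10.2. An ethics modification is also required. Both points are right and are included in the fix.

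**Conclusion.** The concern holds, and the section must be corrected before allocation starts. Section 10.1 is wrong as written: its reason does not apply to the step at which the groups diverge, and it conflicts with 9.1 and 13.2. This conclusion rests on the text and on the count of one splint per participant, not on any simulation.

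The size of the resulting bias cannot be known from the documents. With sequential filling, a drift of half an SD would about double the ANOVA false-positive rate, and a drift of one SD would raise it about fivefold. Both figures depend on the assumed filling order and drift. Confounding by participant characteristics would come on top and has not been quantified.

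**What to change.** Replace the text of 10.1 with wording such as: *After the Visit 1 records are complete, participants are randomised 1:1:1:1 to groups A to D (10 each) from a computer-generated permuted-block list. A supervisor holds the list and releases each allocation only to the dental lab when splint design starts. Participants are analysed in the group to which they were allocated.*

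Then make the related passages consistent:

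- Sections 9.1 and 13.2 can stand, with 9.1 pointing to 10.1 for the method and timing.
- Section 10.2 should say who knows the allocation at the fitting visit, because release to the lab alone may make it possible to keep the operator unaware.
- In 13.1, remove the ambiguity about 40 splints for each group by stating one splint per participant.

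Other ways of generating the list would also do. What is essential is that allocation is random, concealed until the Visit 1 records are complete, and described the same way throughout.

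**Cost:** revised wording, a computer-generated list, and a modification request to the ethics committee, which the Approvals section (8.7) requires before any amendment is implemented. The sample size stays at 40. No extra visits, splints or staff are needed, because every participant already has all the records that any group requires.

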10.2 Blinding & other measures taken to avoid bias (if applicable)

8.4.1 Blinding.

The trial cannot be blinded.

10.2.2 Other measures taken to minimise/avoid bias.

The scanning will be done by an experienced single operator to all participants with the help of a prosthodontic consultant and if needed it will be repeated.

10.3 Intervention Procedures

Intraoral scanning and using the facebow to record the maxillary jaw mount.

Insertion of occlusal splints, fitting them, and doing the occlusal adjustment needed.

10.4 End of Study/Trial Definition

The end of trial is when all data has been collected and the database locked.

8.7 Approvals

The study protocol and other documentation will be submitted to the King's College London Research Ethics Committee and **REMAS** before the start of the study.

All correspondence with the REC will be retained.

Any amendments to the study will be submitted to the King's College London Research Ethics Committee as a modification request through REMAS. Amendments will not be implemented until a favourable opinion is issued.

11 Compliance and withdrawal

11.1 Participant compliance

The participant will be provided by an information sheet explaining the trial procedure and will be asked to sign an informed consent.

11.2 Withdrawal / dropout of participants.

The participants are free withdraw at any point of the project, without having to give a reason.

Withdrawing from the project will not affect you in any way. If so, their data Will be deleted.

11.1 protocol compliance.

[name] will record non-compliance with the protocol if any happened and will email it to supervisors ([name] and [name])

12 Data

12.1 Data to be collected.

Baseline data, including intraoral scans, clinical photographs, and digital facebow, will be obtained for each participant. This data will serve as a reference for both digital and semi-digital occlusal assessments.

12.2 Data handling and record keeping.

The data will be processed under the terms of UK data protection law (including the UK General Data Protection Regulation (UK GDPR) and the Data Protection Act 2018).

- we are not collecting any personal information besides the name on the consent form.
- the participants and their personal information will not be identified during or after the study.
- The data will be achieved for future records as long as the PhD course.
- The data will only be shared within the research team.

Specialist teams within King's College London continually assess and ensure that data is held in the most appropriate and secure way.

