13.3 Interim analysis and data monitoring

13.3.1 Stopping/ discontinuation rules and breaking of randomisation code

For each volunteer, the complete end point of this project will be the final after fitting the splints and doing the occlusal modification needed. After that clinical session they do not need to do any further experiments. Premature discontinuation is defined as volunteers get COVID or they want to withdraw from the research before the end of the project. They will inform the primary researcher ([name]) or the supervisors ([name] and [name]) and they will be removed along with their data if the data have not already been pooled together.

13.3.2 control and assurance.

There is no data monitoring or steering committee set up for this project.

14 Ethical considerations

This study will adhere to ethical standards, and ethical approval will be obtained from the REMAS.

15 Risk Management & Safeguarding

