15.1 Risk Management

No risk to your health or teeth will be applied. Slight discomfort may arise when taking the scans as well as during the fitting of the splint and the participant can choose to stop the procedure at any time.

16 Financing

This trial is funded by the Hashemite university of Jordan.

17 Insurance

The study is sponsored by King's College London (KCL). The sponsor will, always, maintain adequate insurance in relation to the study: KCL through its own professional indemnity (Clinical Trials) & no-fault compensation, in respect of any claims arising because of negligence by its employees, brought by or on behalf of a trial participant.

18 Publication and Dissemination

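### Sections 11.2 and 13.3.1 give conflicting rules for deleting data, 13.3.1 also removes COVID cases who have not asked to leave, and the retention reporting in 13.2 is not assured

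*Combined protocol and SAP*

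**What the plan says.** Four sections of the combined protocol and SAP bear on this.

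- **Section 11.2 (Withdrawal / dropout).** "The participants are free withdraw at any point of the project, without having to give a reason". The consequence follows without any condition: "If so, their data Will be deleted".
- **Section 13.3.1 (Stopping/discontinuation rules).** "Premature discontinuation is defined as volunteers get COVID or they want to withdraw from the research before the end of the project". Of these volunteers it says "they will be removed along with their data if the data have not already been pooled together". Pooling is neither defined nor dated.
- **Section 13.2 (Statistical analysis).** "Patient drop-out data will be collected to calculate retention rates and identify reasons for non-completion". It adds: "The number and proportion of participants who did not complete the trial overall will be reported".
- **Section 15.1 (Risk Management).** Slight discomfort is foreseen during scanning and during splint fitting, and "the participant can choose to stop the procedure at any time".

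For context, section 6.1 takes the second splint scan only once the occlusal adjustments at visit 2 are finished. Section 8.4.1 states that the trial cannot be blinded. Section 13.1 sets 10 participants in each of four groups. The plan states no analysis population, missing-data method, replacement rule or dropout allowance.

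**The concern.** Two operative rules on the same event differ, so staff following the protocol cannot know which data to keep. The choice turns on when data are pooled, a step that the unblinded team controls and that the plan does not schedule. Who is analysed is therefore not fixed in advance.

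The COVID clause removes people who have expressed no wish to leave. An infection is not a reason to doubt a scan already taken, and no other reason is given for discarding it.

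Section 13.2 promises retention rates and reasons for non-completion, while 11.2 deletes a withdrawer's data without saying what, if anything, survives.

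If withdrawal is related to how well the splint fits, the loss is also related to the outcome. With 10 per group, each lost participant is a tenth of a group.

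**Working it through.** **1. The two deletion rules side by side**

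| Event | Section 11.2 | Section 13.3.1 |
|---|---|---|
| Withdraws before pooling | Delete | Delete |
| Withdraws after pooling | Delete | Keep |
| Gets COVID, does not ask to leave, before pooling | Not covered | Delete |
| Gets COVID, does not ask to leave, after pooling | Not covered | Keep |

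The second row is a direct contradiction. The third discards data from a participant who has not withdrawn.

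**2. When can deletion remove a measured outcome?** The outcome needs the post-adjustment scan at visit 2.

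- A participant who stops before that scan, or gets COVID before visit 2, has no outcome under any rule.
- Under 13.3.1, a measured outcome can be lost only between that scan and pooling.
- Under 11.2, it can be lost at any time after the scan.

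Section 13.3.1 also says that each volunteer's own end point is the fitting visit. If the end of the project means that visit, the 13.3.1 window closes at the scan. The pooling condition would then have little to act on, so the wider reading fits the text better. The wording needs settling either way.

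**3. Retention reporting.** Section 9.1 keeps the numbers approached, eligible and agreeing. Section 9.2 logs everyone who accepts. If these records survive a withdrawal, an overall retention rate follows from agreed minus completed. Neither record is said to hold group, stage of withdrawal or reason, and no section says whether the data deleted under 11.2 include log entries. Overall counts are feasible but not guaranteed. Reasons depend on what is volunteered and whether it is kept.

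**4. Size, as illustration only.** The plan's total reproduces: 4 × 10 = 40. There is no power calculation to check, because the plan gives no alpha, power, effect size, SD or dropout rate. The following is therefore assumed: independent normal outcomes with equal variance, no true difference, alpha 0.05, and the four-group ANOVA named in the synopsis.

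- *Shift in a group mean.* Sort 10 standard normal values, drop the largest k, and average the remaining 10 − k. Over 1,000,000 simulated groups the mean is −0.170 for k = 1 and −0.317 for k = 2, a fall of 0.17 or 0.32 SD.
- *Type I error, loss in one group only.* With group sizes 10 − k, 10, 10 and 10 (200,000 runs), the proportion with p < 0.05 is 4.9% for k = 0, 6.7% for k = 1 and 9.7% for k = 2.
- *Other patterns.* Dropping the worst 1 or 2 from both non-facebow groups (A and C) gives about 8.0% or 13.4%. Dropping them from all four groups gives about 8.8% or 11.7%.

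**The case against.** The strongest reply is about mechanism. The only textual link between fit and leaving is the discomfort foreseen at fitting. Someone who stops then has no post-adjustment scan, so deletion takes no final outcome from the analysis. That stands. A reader might infer that the plan removes bad outcomes selectively after they are known, but no section links withdrawal in the period after the scan to fit. Informative loss during fitting is a missing-data problem, and the plan has no method for it. The deletion rule adds to it only by removing the trace that a difficult fitting occurred.

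A reader might also infer that the retention analysis is impossible. It is not. The recruitment record and screening log could supply overall counts, the deleted data could mean only the scans and photographs listed in section 12.1, and 13.2 promises overall figures, not figures by group.

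Larger error rates can be produced. If the worst 1 or 2 are lost from both non-facebow groups and none from the others, a facebow contrast rejects in about 9.2% or 18.0% of null trials. That contrast is not a planned test, and if all groups fit equally well, fit-driven loss has no reason to concentrate in groups A and C. Selective removal of exactly the worst values is an extreme case in a two-visit study of healthy volunteers.

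Finally, deletion may be a promise made to participants, since the information sheet and consent text are not available here. That limits how the rule may be changed. It does not remove the conflict between two sections of the protocol.

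**Conclusion.** The point holds in its textual form. Sections 11.2 and 13.3.1 conflict for anyone who withdraws after pooling. Section 13.3.1 discards not-yet-pooled data from volunteers who merely get COVID. Together they leave the analysis set dependent on an undated step in an unblinded study, and the reporting in 13.2 is not assured.

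Bias in the group comparison is possible but not shown. It requires withdrawal to be related to fit, which the documents do not state. With loss in one group only, the illustrative ANOVA error of 6.7% or 9.7% against a nominal 5% rests on the assumptions listed above and on the most selective removal possible. It shows how sensitive groups of 10 are to one or two lost values and is not a forecast. This should be corrected before any data are deleted, because deletion cannot be undone.

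**What to change.** - Write one data rule into sections 11.2 and 13.3.1, consistent with the information sheet and consent form. Data collected up to withdrawal are kept and analysed in the participant's group, and are erased only on the participant's explicit request. State in advance the cut-off after which erasure is no longer possible, and define pooling or drop the term.
- Remove COVID as a ground for deleting data. Whether infection ends participation is a separate matter, not addressed here.
- For every non-completer, including those whose data are erased, keep a non-identifying disposition line with group, stage reached and any reason volunteered. This secures the reporting in 13.2.
- State the analysis set. List separately the splints whose adjustment was stopped early.

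The cost is wording in two sections, any matching change to the participant documents, and the ethics modification request that section 8.7 requires for any amendment. No further participants, visits or procedures are needed, and a participant who asks for erasure before the cut-off still gets it. Participants who consented under a promise of deletion must be handled under the terms they were given.
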